Subjects will check in to the clinic in the morning on Day -2 for a 9-day In-house Period. They will receive standardized meals throughout their inpatient stay. Subjects will be connected to an ABPM system, and overnight measurements will be taken to familiarize the subjects with the device. ABPM measurements will continue throughout Day 4. Only 24-hour monitoring data from Day -1 will be used for the baseline monitoring evaluation.

In the morning of Day -1, subjects will get connected to a Holter ECG for 24-hour measurements and will continue these until the morning of Day 4. Only 24-hour monitoring data from Day -1 will be used for the baseline monitoring evaluation.

Subjects will be randomized to a single SC injection of HM15211 or placebo.

On Day 1, the active study drug or placebo, will be administered in the morning at approximately 08:00 hours (t=0), SC into the abdominal wall by qualified study staff. Measurements of vital signs, PK and laboratory parameter will be performed for safety evaluation.

ABPM and Holter ECG monitoring will be continued until the morning of Day 4 for the post-dose evaluation. 24-hour monitoring evaluations will be performed together with available PK data, in order to determine the best time period for 24-h monitoring period around PK_{peak}.

Subjects will continue to stay in-house for safety evaluations and PK. They will be released from the clinical research unit (CRU) in the morning of Day 7 and will return for two outpatient visits on Day 10 and 17.

Outpatient Visits:

Subjects will return to the CRU on Days $10 (\pm 1)$ and $17 (\pm 1)$ for two outpatient visits. Blood samples for PK analysis will be collected, additional safety assessments as stated in Table 16-1 will occur.

Follow-up Visit:

A follow-up visit will take place on Day 30 (\pm 2).

	Time points for study procedures and sample collections for PK measurements will be specified in detail in Table 16-1 of the protocol.		
	Safety assessments will occur throughout the duration of the study.		
Treatment	Sample Treatment Schedule:		
	Cohorts	Number of Subjects	Treatment Period
	Cohort 1	N=6	HM15211 - 0.01 mg/kg
		N=2	Placebo
	Cohort 2	N=6	$HM15211 \le 0.02 \text{ mg/kg}$
	Conort 2	N=2	Placebo
	Cohort 3	N=6	$HM15211 \le 0.04 \text{ mg/kg}$
	Condition	N=2	Placebo
	Cohort 4	N=6	$HM15211 \le 0.08 \text{ mg/kg}$
	Conort 4	N=2	Placebo
	Cohort 5	N=6	$HM15211 \le 0.16 \text{ mg/kg}$
	Condition	N=2	Placebo

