4.5 Dose Escalation Algorithm

The proposed dose escalation algorithm for HM15211 may include the following steps:

Table 4-2 Sample Allocation and Dose Escalation

Cohorts	Number of Subjects	Treatment Period	
Cohort 1	N=6	HM15211- 0.01 mg/kg	
	N=2	Placebo	
Cohort 2	N=6	$HM15211 \le 0.02 \text{ mg/kg}$	
	N=2	Placebo	
Cohort 3	N=6	$HM15211 \le 0.04 \text{ mg/kg}$	
	N=2	Placebo	
Cohort 4	N=6	$HM15211 \le 0.08 \text{ mg/kg}$	
	N=2	Placebo	
Cohort 5	N=6	$HM15211 \le 0.16 \text{ mg/kg}$	
Conort	N=2	Placebo	

Each subject will be randomized to HM15211 or placebo according to the table above. The dose will be 0.01 mg/kg, based on the body weight measured prior to dosing. For dose calculation and rounding, please refer to the Operational Manual/Pharmacy Manual.

After at least 6 subjects ($n \ge 4$ subjects on active drug HM15211) in each cohort have completed at least Day 10, safety and available PK data will be reviewed and a dose decision/ dose escalation decision for the subsequent cohort will be made by the Sponsor and the Investigator. Doses between cohorts will not exceed a 2-fold increase relative to the specified doses stated in the Table 4-3 above. Following the dose escalation decision, the procedures for the subsequent cohorts will be identical to those described above.

Adjustments to the procedures/cohorts may occur after the review of available safety and PK data:

- Adjustments to the number of study cohorts may occur: Additional cohorts may
 be enrolled and proceed at a higher or a lower dose. If deemed appropriate by the
 investigator and sponsor, there may be more than one cohort investigated at the
 same dose level.
- Adjustments to the 24-hr BP and HR monitoring: After the evaluation of the first cohort, tests may be rescheduled, or measurement periods may be focused on specific days to capture the 24-h measurement around the PK_{peak}.
- Adjustments to the visit schedule: If PK data suggest, additional sampling times and/or outpatient visits may be added to the study schedule.

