6.2 Study Description

Each subject will undergo the following procedures during the study:

Screening Visit:

Before the screening takes place, potential subjects for the trial will be provided with written and oral information about the trial and the procedures involved. Subjects must sign the informed consent form (ICF) prior to entering the study. Please see section 9.1.1 for further details.

The screening visit will be performed up to 28 days prior to the first dosing day, to identify eligible subjects for the study. All assessments performed at the screening visit are stated in Table 16-1 and will be recorded in the electronic case report form (eCRF). Please see section 9.1.2 and 11.2 for further details.

In-house Period:

Subjects will check in to the clinical research unit (CRU) in the morning of Day -2 for a 9-day in-house period. They will receive standardized meals throughout their in-house stay. A 12-lead standard ECG will be performed. Subjects will be connected to an ABPM system for measurement of blood pressure (BP), and measurements will be started overnight on Day -2 to familiarize the subjects with the device. Measurements will continue until the morning of Day 4.

In the morning of Day -1, subjects will get connected to a Holter ECG for continued measurement of the heart rate activity until the morning of Day 4.

Only 24-hour monitoring data from Day -1 to Day 1 will be used for the monitoring evaluation as baseline assessments for ABPM and Holter ECG monitoring. For measuring timepoints, please see sections 9.1.14 and 9.1.15.

Subjects will be randomized to a single SC injection of HM15211 or placebo. Randomization will take place as close to the drug administration as possible.

On Day 1, after an \geq 10 h overnight fast, subjects will be dosed with HM15211or placebo at approximately 08:00 hours (t=0), through SC injection into the abdominal wall by qualified study staff. Measurements of vital signs, ECG, blood sampling for PK and PD analyses, local injection site evaluation, and laboratory parameter will be performed for safety evaluation, at timepoints stated in Table 16-1.

ABPM and Holter ECG monitoring will be continued until the morning of Day 4 for the post-dose evaluation. 24-hour monitoring evaluations will be performed together with available PK data, in order to determine the best time period for 24-h monitoring period around PK_{peak}.

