6.3 Rationale for Study Design and Endpoints

This SAD study will assess the safety and tolerability as well as PK of HM15211 as primary objectives.

Cohorts will be assessed in ascending order, but may overlap, to determine a clinically appropriate dose for the subjects and will include the comparison with placebo.

Randomization is used to avoid bias introduced through an association between study drug allocation order and subject characteristics.

A double-blind design has been chosen to avoid bias and to maintain the blind between the administration of the study drug and placebo.

Healthy obese subjects will participate in the study, as these subjects are an important target population for the novel triple agonist. Enrollment criteria will favor the target population, as body mass index will be limited to ≥ 30 to ≤ 40 kg/m².

After PK modeling, C_{max} is expected to be reached approximately 3 days after dosing. As this is a first-in-human study, measurements for the assessment of cardiovascular events will start right after dosing and will continue until Day 4. After evaluation of the PK values in the initial cohort(s), the monitoring period will be adjusted, to ensure that the 24-h period around the PK_{peak} is captured.

The proposed PK endpoints are well-established, commonly used parameters to characterize pharmacological profiles of drugs. For the PK endpoints, blood samples for determination of HM15211 will be analyzed using a validated assay.

This is an exploratory study. No formal sample size calculation and no statistical hypothesis testing will be performed.

The study will be conducted at a specialized early phase research centre, where the subjects will be under supervision of physicians, research nurses and additional medical staff experienced in conducting early phase clinical studies investigating new metabolic compounds.

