9.1.6 Vital Signs

Vital signs will include body temperature (*aural*), supine and standing blood pressure (supine BP after 5 minutes resting, standing BP within 3 minutes in upright position), respiration rate and pulse rate (after 5 minutes resting). Vital sign measurements will be performed at days indicated in the Table 16-1.

Body temperature: Assessments will be performed once daily, as stated in the Table 16-1. Measurements may be taken more frequently, if deemed necessary by the Investigator. Measurement on Day -1 will be performed as baseline assessment. Measurements will continue throughout the study. Timepoints must not interfere with ABPM measurements.

Blood pressure:

Supine and standing assessments will be performed. Measurements will be taken once at Screening and once on Day -2 and twice (morning and evening) on Day -1. The rest of the measurements will follow the following sampling schedule: On Day 1, measurements will be performed pre-dose and at 4, 8 and 12 hours post-dose. On Day 2 at 24 and 36 hours, on Day 3 at 48 hours, on Day 4 at 72 hours, on Day 5 at 96 hours, on Day 6 at 120 hours, on Day 7 at 144 hours post-dose with a sampling window of \pm 15 min for each timepoint. Additional measurements will be taken on Day 10 at 216 hours (\pm 1 day), on Day 17 at 384 hours (\pm 1 day), and on Day 30 at 696 hours (\pm 2 days) post-dose.

Measurements will be performed on the arm that is not connected to the ABPM system. Timepoints must not interfere with the ABPM measurements.

Pulse rate and respiration rate: Assessments will be performed as stated in the Table 16-1 at timepoints for blood pressure measurements. Pulse rate will be assessed in combination with both, supine and standing blood pressure measurements. Respiratory rate will be assessed at timepoints of supine blood pressure measurements.

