9.1.11 ECG Procedure

All ECG's throughout this study will be performed as standard triplicate 12-lead ECG's, except the ECG at Screening. ECG's will be recorded after 5 minutes in a supine position. Only the Triplicate ECG's will be recorded at least 1 minute apart from each other, not exceeding a time period of 5 minutes for the completion of all three ECG's.

The Investigator (or designee) will interpret the ECG's by use of an electronic measurement using the following categories: within normal limits, abnormal but not clinically significant, or abnormal with clinical significance. ECG's are performed according to the Table 16-1. The following parameters will be recorded from the subject's ECG trace: heart rate, QT interval, PR interval, QRS interval, R-R interval, and QTcF (corrected).

The Investigator will be responsible for assessing the accuracy of the electronic QTc interval recording using Fridericia correction formula

• Fridericia correction: QTcF = QT ÷ cube root of the R-R interval (where R-R is the duration of the entire cardiac cycle)

When ECGs are to be collected at the same time point as a blood collection, ECGs should be collected first to avoid any artificially increased heart rates due to the blood collection.

ECG measurements are to be collected during screening and on Day -2 before subjects are connected to the ABPM device. Additionally, ECG measurements are taken on Day 4, after ambulatory devices (Holter and ABPM) are removed, and Days 5, 7, 10, 17 and 30.

In some cases, it may be appropriate to repeat abnormal ECGs. If a machine-read QTc value is prolonged, repeat measurements may not be necessary if the Investigator's interpretation determines that the QTc value is in the acceptable range.

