9.1.14 ABPM

The 24-hour blood pressure will be measured by an ABPM device. A validated, reliable, automated, and accurate monitor will be used with a storage function. Blood pressure measurements will be started overnight on Day -2 to familiarize the subjects with the device. During this period, measurements will be taken every 2 hours until the morning of Day -1.

The baseline assessment period will start in the morning of Day -1 until Day 1. Measurements will be taken hourly up to 14 hours and then 2-hourly until 24 hours.

The post-dose assessment period will start in the morning of Day 1. Measurements will be taken hourly up to 14 hours and then 2-hourly until 24 hours every day (for every 24-hour period), until the morning of Day 4.

Time points stated in the Table 16-1. Adequate cuff size will be documented for each subject, after determination of the patient's non-dominant arm circumference. Subject's bedtime and awakening will be recorded to divide the downloaded data into diurnal and nocturnal values. Depending on available PK and safety data, timepoints for measurements may be adjusted for the following cohorts.

Specifications about the ABPM model will be described in the Operational Manual and ABPM Procedure Manual, as well as detailed instructions of blood pressure frequency, data management and medical review.

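### In the first cohort(s), ABPM and Holter recording stops at about 72 h, the predicted time of Cmax, and the protocol is inconsistent on when ABPM ends and on whether the later adjustment is firm

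*Protocol*

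**What the plan says.** Section 5.1 lists 24-hour ABPM (mean day- and night-time blood pressure) and 24-hour Holter (heart rate and its variability) among the primary safety endpoints.

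**End of recording.** Section 6.2 says that "ABPM and Holter ECG monitoring will be continued until the morning of Day 4", and that these recordings will be read with the PK data to choose the best 24 h around the peak. Section 9.1.14 has ABPM readings hourly up to 14 h and then "2-hourly until 24 hours every day (for every 24-hour period), until the morning of Day 4". Section 9.1.11 states that "ECG measurements are taken on Day 4, after ambulatory devices (Holter and ABPM) are removed", and footnote 2 of Table 16-1 agrees. Section 2.0 differs: its in-house description says "ABPM measurements will continue throughout Day 4", then further down ends both devices on the morning of Day 4.

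**Predicted peak.** Section 6.3 says that Cmax "is expected to be reached approximately 3 days after dosing".

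**Later adjustment.** Section 6.3 states that, once PK from the initial cohort(s) is known, the period *will* be changed so that the 24 h around the peak is captured. Section 4.5 says "After the evaluation of the first cohort, tests may be rescheduled", as does Section 2.0. Section 9.1.14 and footnote 4 of Table 16-1 are also permissive.

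**The concern.** The stated aim is to capture blood pressure and heart rate over the 24 h around the peak, but the default recording ends at the predicted peak. In the first cohort(s), any effect that appears or persists after about 72 h would have no ambulatory data beside it, although PK sampling continues at 96 h and 144 h (Table 9-2). The recordings meant to help choose the best window cannot show what happens after they stop.

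Comparability is also at stake. Section 12.2.5 pools placebo subjects across cohorts for safety, and there are 2 per cohort. Section 4.5 allows recording to be focused on specific days. If the window is moved rather than extended, the earlier placebo and active subjects have no data on the new days. The conflicting wording leaves open when ABPM ends and whether the adjustment must happen at all.

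**Working it through.** **Inputs.** Dosing is at about 08:00 on Day 1 (Section 6.2). Section 9.1.6 ties study days to hours: "on Day 3 at 48 hours, on Day 4 at 72 hours". Predicted Tmax is about 3 days (Section 6.3). The protocol does not define the window around the peak, so a centred one, Tmax ± 12 h, is assumed.

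**End of recording.** Morning of Day 4 = (4 − 1) × 24 = 72 h, which agrees with Section 9.1.6. Predicted Tmax = 3 × 24 = 72 h. The two coincide.

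**Coverage.** For recording from 0 to E, hours covered = max(0, min(Tmax + 12, E) − (Tmax − 12)). At Tmax 72 h the window is 60-84 h. With E = 72 the overlap is 72 − 60 = 12 h, or 50%.

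| Tmax (h) | E = 72 | E = 84 | E = 88 | E = 96 |
|---|---|---|---|---|
| 60 | 24 | 24 | 24 | 24 |
| 66 | 18 | 24 | 24 | 24 |
| 72 | 12 | 24 | 24 | 24 |
| 78 | 6 | 18 | 22 | 24 |
| 84 | 0 | 12 | 16 | 24 |

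E = 88 (midnight) and E = 96 (08:00 on Day 5) are two ways to read ABPM running through the whole of Day 4. Under either, ABPM covers the centred window at Tmax 72 h and only Holter falls short.

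**Which half is missing.** The covered hours, 60-72 h, run from about 20:00 to 08:00 and are mostly night. Under the Section 9.1.14 scheme, ABPM readings fall at 60, 61, 62, 64, 66, 68, 70 and 72 h, which is 8 readings. Continuing to 84 h adds the 12 hourly readings from 73 to 84 h, giving 20. So 8 of 20 are taken, and those lost are daytime readings.

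**How close to peak the recorded day is.** As an illustration, take a one-compartment first-order model with Tmax 72 h. With equal absorption and elimination rates of 1/72 per h (half-life 49.9 h), C(t)/Cmax = (t/72) × exp(1 − t/72).

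- t = 48: 0.667 × 1.396 = 0.93
- t = 96: 1.333 × 0.717 = 0.96

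Half-lives of 36 and 86 h, about the ends of the animal range in Section 4.3, give values within 0.01 of these. On concentration alone, the recorded day (48-72 h) and the unrecorded day (72-96 h) are similar. What is lost is information on late-peaking subjects and on effects that lag concentration.

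**Wording side by side.**

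| Point | One reading | Other reading |
|---|---|---|
| End of ABPM | Whole of Day 4: one sentence in 2.0 | Morning of Day 4: 2.0 (later), 6.2, 9.1.14; removal before the Day 4 ECG: 9.1.11, Table 16-1 footnote 2 |
| End of Holter | None | Morning of Day 4: 2.0, 6.2 |
| Adjustment | Firm: 6.3 | Optional: 2.0, 4.5, 9.1.14, Table 16-1 footnote 4 |

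**The case against.** The strongest reply is that this is an explained adaptive choice. Section 6.3 says that recording starts at dosing because the study is first-in-human, and that the period will be adjusted once PK is known. Capturing the peak window is then a goal for later cohorts, not a promise for the first, which receives the lowest dose. This stands as far as it goes: the half coverage belongs to the initial schedule and would persist only if the permissive wording were followed and nothing changed.

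It also stands that the 50% depends on a centred window and a Tmax of exactly 72 h, that 48-72 h is already near peak for a typical subject, and that cardiovascular monitoring does not cease. Spot blood pressure and pulse continue at 72, 96, 120 and 144 h and at later visits (Section 9.1.6), and triplicate ECGs follow on Days 4, 5, 7, 10, 17 and 30 (Section 9.1.11). These do not, however, give 24-h means, night-time values or heart rate variability. The ambulatory data are summarised descriptively, with no hypothesis test.

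Two stronger readings are tempting. A reader might infer that about half of subjects would peak after the devices come off, but the protocol gives only an approximate predicted Tmax and no distribution. A reader might also infer that the schedule is poor because most of the exposure falls after recording stops. In any one-compartment first-order model at most 1 − 2/e = 26.4% of the AUC lies before Tmax, so that observation describes the model and not this schedule.

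**Conclusion.** The point holds in a limited form. Under the initial schedule both devices stop at about 72 h, the predicted time of Cmax, so the first cohort(s) lack ambulatory data after the predicted peak. Coverage of a centred 24-h window is 12 of 24 h at Tmax 72 h, 24 h at Tmax 60 h and none at Tmax 84 h.

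The contradiction on end time concerns ABPM only. If the whole-of-Day-4 wording governs, the ABPM gap at Tmax 72 h disappears and the two devices stop at different times. If the morning wording governs, the gap applies to both. Either way the text needs correcting. The conflict over a firm or optional adjustment is separate and also real.

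A reader might infer that every cohort misses the peak, or that later cohorts will be non-comparable. The documents support neither: Section 6.3 plans a change, and an adjustment could extend the window rather than move it. The point merits a change because these are listed primary safety endpoints and the remedy is cheap. It does not undermine the study.

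**What to change.** Required: state one end time for both devices and use it in Sections 2.0, 6.2, 6.3, 9.1.14 and 9.1.11 and in the footnotes to Table 16-1. Reconcile the firm adjustment in Section 6.3 with the permissive wording in Sections 2.0, 4.5 and 9.1.14 and footnote 4, including whether it follows the first cohort or the initial cohort(s).

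Recommended: from cohort 1, extend the initial recording past the predicted peak. Recording to 84 h covers a centred window at Tmax 72 h; recording to 96 h completes a 24-h period in the Section 9.1.14 scheme and tolerates Tmax up to 84 h. The Day 4 ECG instruction then needs a matching edit, for example a short disconnection. In later cohorts, add days to this common period rather than replace it, so that pooled placebo and cross-cohort summaries rest on the same days.

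Cost: 12 to 24 h more device wear per subject, a brief interruption for the Day 4 ECG, and the text edits. No extra visit is needed, because subjects stay in-house until the morning of Day 7.

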6.3 Rationale for Study Design and Endpoints

This SAD study will assess the safety and tolerability as well as PK of HM15211 as primary objectives.

Cohorts will be assessed in ascending order, but may overlap, to determine a clinically appropriate dose for the subjects and will include the comparison with placebo.

Randomization is used to avoid bias introduced through an association between study drug allocation order and subject characteristics.

A double-blind design has been chosen to avoid bias and to maintain the blind between the administration of the study drug and placebo.

Healthy obese subjects will participate in the study, as these subjects are an important target population for the novel triple agonist. Enrollment criteria will favor the target population, as body mass index will be limited to ≥ 30 to ≤ 40 kg/m².

After PK modeling, C_{max} is expected to be reached approximately 3 days after dosing. As this is a first-in-human study, measurements for the assessment of cardiovascular events will start right after dosing and will continue until Day 4. After evaluation of the PK values in the initial cohort(s), the monitoring period will be adjusted, to ensure that the 24-h period around the PK_{peak} is captured.

The proposed PK endpoints are well-established, commonly used parameters to characterize pharmacological profiles of drugs. For the PK endpoints, blood samples for determination of HM15211 will be analyzed using a validated assay.

This is an exploratory study. No formal sample size calculation and no statistical hypothesis testing will be performed.

The study will be conducted at a specialized early phase research centre, where the subjects will be under supervision of physicians, research nurses and additional medical staff experienced in conducting early phase clinical studies investigating new metabolic compounds.

